**Revision History**

Revision Number	Release Date	Section	Change	Reason for Change
AA	NA	NA	NA	Pre-release version

## 2. Protocol Synopsis

Objective(s)	The primary objective is to test the hypothesis that post-MI diabetic patients with relatively preserved ejection fraction of 36-50% will have a survival benefit from a subcutaneous implantable cardioverter defibrillator (S-ICD).
Planned Indication(s) for Use	The EMBLEM S-ICD System is intended to provide defibrillation therapy for the treatment of life-threatening ventricular tachyarrhythmias in patients who do not have symptomatic bradycardia, incessant ventricular tachycardia, or spontaneous, frequently recurring ventricular tachycardia that is reliably terminated with anti-tachycardia pacing.
Test Device System	
 
• EMBLEM™ S-ICD Pulse Generator (Model A209) or later generation commercially available BSC S-ICD pulse generator
 
• EMBLEM™ S-ICD Subcutaneous Electrode (Model 3401), Q-TRAK Electrode (Model 3010) or later generation market approved BSC S-ICD electrode
 
• EMBLEM™ S-ICD Electrode Insertion Tool, (Model 4711), Q-GUIDE Electrode Insertion Tool Model (Model 4010), or later generation market approved BSC electrode insertion tool
 
• EMBLEM™ S-ICD Programmer, (Model 3200) or other market approved programmer capable of interrogating BSC S-ICD Systems
 
• Additional implant accessories used in the implant procedure will be considered to be part of the device system.
 

Control	Conventional medical therapy (CMT).
Study Design	Prospective, multicenter, international, randomized, controlled trial.
Planned Number of Subjects	1800 subjects to be enrolled according to the sample size assumptions.

 Over the course of this study, new model numbers of each device may be introduced. The intention of this protocol is to allow the use of newer Boston Scientific subcutaneous implantable cardioverter defibrillator (S-ICD) system components that are market approved by the regulatory authorities in the country of the investigative site.

Planned Number of Sites/Countries	Approximately 100 sites in the US, EU and Israel with a maximum of 150.
Primary Endpoint	The primary endpoint is all-cause mortality.
Additional Objectives	In all randomized subjects the following analyses will be performed: 
 
• All-cause mortality and sudden cardiac death in various subgroups including sex, race, age continuous and dichotomized at 75 years, duration of diabetes, presence vs. absence of insulin therapy, HbA1c dichotomized at 8%, LVEF continuous and dichotomized at 40%, and other relevant subgroups
 
• Healthcare utilization assessed through adverse event reporting
 

Additional Pre-Specified Analyses	In subjects randomized to S-ICD the following analyses will be performed: 
 
• Frequency and outcomes of S-ICD Inappropriate Shocks
 
• Frequency and outcomes of S-ICD treated ventricular tachycardia (VT) and ventricular fibrillation (VF)
 
• Frequency and outcomes of S-ICD device complications, including but not limited to: infection, device malfunction and electrode movement
 

Method of Assigning Patients to Treatment	Subjects will be randomized 2:1 (S-ICD:CMT). Randomization will occur electronically using the clinical data collection system.
Follow-up Schedule	
 
• Screening and Consent
 
• Baseline data collection
 
• Implant procedure (device subjects only)
 
• 1 month visit (in-clinic visit for S-ICD subjects and phone contact for CMT subjects)
 
• 6 month phone contact (conduct annually thereafter at months 18, 30, 42, etc.)
 
• 12 month visit (conduct annually thereafter at months 24, 36, 48, etc.) 
 
○ S-ICD Arm 12 Month in-clinic follow-up
 
○ CMT Arm 12 Month phone follow-up
 
 
 

Study Duration	The study is expected to enroll over a 48 month period with an average of 2.6 years of follow-up. Note: the length of the study is based on the accumulation of endpoint events and the hazard ratio.
Eligibility Criteria	Note: The most recent evaluations, measurements or test results in the medical record must be used to assess inclusion and exclusion criteria.


Key Inclusion Criteria
	
 
• Age <math>\geq</math> 65 years on date of consent
 
• Diabetes mellitus treated with oral hypoglycemic agents, non-insulin injectable and/or insulin for the past 3 calendar months or longer prior to consent date
 
• LV ejection fraction (LVEF) of 36-50% documented by imaging (preferably by MRI or echocardiographic methods), within 12 calendar months before consent date and at least 3 calendar months after most recent MI, PCI or CABG
 
• One or more clinically documented, enzyme-positive myocardial infarctions, more than 3 calendar months prior to consent date*. 
 
○ If enzyme information and clinical documentation is not available, there must be a clear evidence of prior silent myocardial infarction identified as either new pathologic Q waves on ECG or imaging documentation of an infarcted area (left ventricular angiography/ nuclear scan/ MRI)* 
 
* MI qualification based on the Universal Definition of MI
 
 
 
 
 
• Qualifying 12-lead ECG within 6 calendar months before consent date and at least 3 calendar months after most recent MI, PCI or CABG 
 
* The qualifying ECG can be sinus rhythm or atrial fibrillation (patients with persistent or permanent atrial fibrillation should have a controlled ventricular response <math><100</math> bpm on consent date)
 
*QRS duration on the qualifying ECG <math>\geq 90</math> msec
 
 
 
• Passing S-ICD Screening ECG performed per applicable user's manual on or after the consent date that identifies one or more qualifying S-ICD sensing vectors
 


Key Exclusion Criteria
	
 
• Ejection fraction <math>>50\%</math> or <math><36\%</math> within 12 calendar months prior to consent date and at least 3 calendar months after the most recent MI, PCI or CABG
 
• Existing guideline based indication for an ICD, pacemaker, CRT, or CRT-D therapy
 
• Existing or previously implanted ICD, CRT, CRT-D, or pacemaker device system
 
• Active infection at the time of consent
 
• Contraindication for S-ICD implantation according to the S-ICD pulse generator (PG) User's Manual
 
• Hemodialysis and/or peritoneal dialysis at the time of enrollment
 
• New York Heart Association Class IV in the past 3 calendar months prior to or at the time of consent date
 
• Coronary artery bypass graft surgery or percutaneous coronary intervention (balloon and/or stent angioplasty) within 3 calendar months prior to the consent date
 
• Enzyme-positive myocardial infarction or silent myocardial infarction diagnosed within 3 calendar months prior to the consent date
 

	
 
• Unstable angina with need for outpatient treatment or hospitalization (change/addition of anti-anginal medication and/or coronary revascularization), within 3 calendar months prior to the consent date
 
• Angiographic evidence of coronary disease in a patient that is a candidate for coronary revascularization and is likely to undergo CABG or PCI in the next 3 calendar months
 
• High risk for arterial embolism (e.g. presence of mobile left ventricular thrombus)
 
• Hemodynamically significant congenital heart disease, aortic valvular heart disease, or amyloid heart disease
 
• Baseline body mass index <math>> 45 \text{ kg/m}^2</math>
 
• On a heart transplant list or likely to undergo heart transplant within one calendar year
 
• Presence of any other disease, other than the subject's cardiac disease, that in the opinion of the investigator is likely to significantly reduce the patient's likelihood of survival for the duration of the trial (e.g. cancer, liver failure).
 
• Unwillingness or inability to cooperate with the protocol
 
• Resides at such a distance from the enrolling site so travel to follow-up visits would be unusually difficult
 
• Reversible causes of heart disease (e.g. viral myocarditis or tachycardia induced cardiomyopathy)
 
• Participation in other clinical trials (observational registries are allowed with approval from the CDC)
 
• Does not anticipate residing in the vicinity of the enrolling site for the duration of the trial
 
• Unwillingness to sign the consent for participation
 

Statistical Methods	
Primary Statistical Hypothesis	Post-MI diabetes patients with a relatively preserved left ventricular ejection fraction will have reduced mortality from S-ICD as compared to CMT.
Statistical Test Method	Wang-Tsiatis group sequential design based on monitoring the log-rank statistic for time-to-death, with stochastic curtailment based on conditional power and sample size re-estimation based on overall recruitment, withdrawal, and event rates.
Sample Size Parameters	1800 patients are expected to yield a maximum of 454 deaths, which provides 80% power at a two-sided significance level of 5% to detect a HR of 0.75.

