#### **12.3.1. Other Objectives/Measurements**

The secondary objective of the study will evaluate the effects of the S-ICD on all-cause mortality in various subgroups and on sudden cardiac death. Sudden cardiac death will be analyzed using methods similar to those for all-cause mortality, except that they will be performed without adjustment for the sequential design. Sudden cardiac death events in the study will be independently adjudicated by the Mortality Events Committee using the Hinkle-Thaler criteria (see Appendix 28.4).

The pre-specified subgroups include but are not limited to: gender, race, age continuous and dichotomized at 75 years, duration of diabetes, presence versus absence of insulin therapy, HbA1c < 8% or ≥ 8%, LVEF continuous and dichotomized at 40%, MADIT II risk score subgroups. For each subgroup analysis, the Cox proportional-hazards regression analysis will be used to evaluate differences between subgroups in the hazard ratios (S-ICD vs. CMT). The baseline covariate or stratum and its interaction with treatment group will be added to the regression model and a test for significant interaction carried out. Each analysis will be stratified by enrolling site, where appropriate. These analyses will be done without

adjustment for the sequential design. Subgroup analyses are further described in section 12.3.3.

Pre-specified tertiary analyses include the following:

1. Frequency and outcomes of S-ICD treated episodes of ventricular tachycardia (VT) and ventricular fibrillation (VF).
2. Frequency and outcomes of S-ICD inappropriate shocks.
3. Frequency of S-ICD device complications, including but not limited to: infection, device malfunction and electrode movement.
4. Healthcare utilization assessed through adverse event reporting.

Tertiary analyses will be descriptive and exploratory. Detailed statistical methods for these outcomes will be presented in a Statistical Analysis Plan (SAP) prior to study termination.

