**Table 19.1-1 Potential Adverse Events for Implantation of the S-ICD System**

Potential Adverse Events for Implantation of the S-ICD System*	
Acceleration/induction of atrial or ventricular arrhythmia	Inability to defibrillate or pace
Adverse reaction to induction testing	Inappropriate post shock pacing
Allergic/adverse reaction to system or medication	Inappropriate shock delivery
Bleeding	Infection
Conductor fracture	Keloid formation
Cyst formation	Migration or dislodgement
Death	Muscle/nerve stimulation
Delayed therapy delivery	Nerve damage
Discomfort or prolonged healing of incision	Pneumothorax
Electrode deformation and/or breakage	Post-shock/post-pace discomfort
Electrode insulation failure	Premature battery depletion
Erosion/extrusion	Random component failures
Failure to deliver therapy	Stroke
Fever	Subcutaneous emphysema
Hematoma/seroma	Surgical revision or replacement of the system
Hemothorax	Syncope
Improper electrode connection to the device	Tissue redness, irritation, numbness or necrosis
Inability to communicate with the device	

Note: If any adverse events occur, invasive corrective action and/or S-ICD system modification or removal may be required.
 
Patients who receive an S-ICD system may develop psychological disorders that include, but are not limited to, the following:
 
 
• Depression/anxiety
 
• Fear of device malfunction
 
• Fear of shocks
 
• Phantom shocks
 
	

\* These events are documented within the physician manual for the EMBLEM S-ICD Pulse Generator User's Manual.

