## **20. Safety Reporting**

### **20.1. Reportable Study Events**

Any reportable event(s), experienced by the study subject after enrollment (defined in section 10.1 as consented and randomized), must be recorded in the electronic data capture system. It is the responsibility of the investigator to determine if the event meets the criteria and report the event to the sponsor per protocol requirements.

For the purpose of this study, relevant reportable events are defined as:

- Device and/or procedure related adverse events (serious and non-serious)
- Unanticipated Adverse Device Effects/Unanticipated Serious Adverse Device Effects previously not defined in the User's manual
- Adverse events associated with cardiovascular conditions (serious and non-serious)
- Serious adverse events, regardless of cause
- Device Deficiencies

Underlying diseases are not reported as AEs unless there is an increase in severity or frequency during the course of the investigation.

Refer to **Section 19** for the known risks associated with the study device(s).

Note: Death should not be recorded as an adverse event. Death should be recorded as an outcome of only one (1) serious adverse event.

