### **20.3. Relationship to Study Device(s)**

The Investigator must assess the relationship of the AE to the study device as related or unrelated. See criteria in Table 20.3-1:

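### Serious and cardiovascular adverse events are collected in both randomised arms, but no by-arm summary of them is pre-specified, so an excess of stroke, syncope, infection or bleeding over CMT is not estimated

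*Combined protocol and SAP*

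**What the plan says.** **Collection.** Section 20.1 makes reportable, for every enrolled subject, "Serious adverse events, regardless of cause" and adverse events linked to cardiovascular conditions, serious or not. Section 11.5 starts adverse event collection once a subject is consented and randomised. Table 11.2-1 schedules it at each CMT follow-up contact. Section 11.9.1 requires an annual record review in the CMT arm, with hospitalizations entered on the adverse event form.

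**Analysis.** The synopsis, under "In subjects randomized to S-ICD the following analyses will be performed", lists inappropriate shocks, treated VT/VF and "Frequency and outcomes of S-ICD device complications, including but not limited to: infection, device malfunction and electrode movement". Sections 6.3 and 12.3.1 repeat these as tertiary analyses; in 12.3.1 the last item reads "Frequency of S-ICD device complications, including but not limited to: infection, device malfunction and electrode movement". For all randomised subjects, the only item built on adverse event data is "Healthcare utilization assessed through adverse event reporting". Section 12.3.1 calls the tertiary analyses descriptive and exploratory and leaves their detailed methods to a later SAP.

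**Listed risks.** Table 19.1-1 includes stroke, syncope, infection and bleeding, as well as "Acceleration/induction of atrial or ventricular arrhythmia".

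**The concern.** Stroke, syncope, infection and bleeding will occur in post-infarction diabetic patients aged 65 or over whether or not they carry a device. For a single case, the device's part can seldom be settled. A device effect shows as a higher rate in the S-ICD arm than in the CMT arm. Randomisation makes that comparison possible and the data are collected, but the plan does not ask for it.

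The trial asks whether a prophylactic implant should be offered to a new population. Section 19.6 states that the projected benefit far exceeds the risks. As planned, the report would set a randomised mortality effect beside a count of device harms that has no control group.

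**Working it through.** The plan states no figure on this point, so the check is mainly a comparison of sections. The arithmetic only shows what the missing analysis could deliver.

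**1. Events collected against analyses planned**

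| Item | Collected in both arms? | Planned analysis | Population |
|---|---|---|---|
| All-cause mortality | Yes | Group-sequential log-rank test, with a boundary in each direction (12.1.1.3) | All randomised |
| Hospital use | Yes, on the adverse event form | Healthcare utilization, descriptive | All randomised |
| Inappropriate shocks, treated VT/VF | Device records, S-ICD only | Frequency and outcomes | S-ICD |
| Device complications | S-ICD only by nature | Frequency (and outcomes, in the synopsis) | S-ICD |
| Any serious adverse event | Yes (20.1) | None by arm | – |
| Serious stroke, syncope, infection, bleeding | Yes (20.1) | None by arm | – |

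Sections 12.3.3 to 12.3.6 (subgroups, pooling, multivariable models, baseline table) do not fill the last two rows. The deferral to a SAP in 12.3.1 covers the four tertiary items only, and a general adverse event comparison is not one of them.

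**2. Precision of a by-arm comparison**

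Inputs: 1,800 subjects randomised 2:1 (synopsis), so 1,200 S-ICD and 600 CMT. The event risks p are assumptions.

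With the same risk in both arms, SE = √[p(1−p)(1/1200 + 1/600)] = √[p(1−p)/400], and the 95% half-width is 1.96 × SE.

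For the excess detectable with 80% power (two-sided 5%), let q be the S-ICD risk and p̄ = (1200q + 600p)/1800. Solve

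q − p = 1.96 √[p̄(1−p̄)/400] + 0.84 √[q(1−q)/1200 + p(1−p)/600].

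Example at p = 5%, q = 8.6%: p̄ = (103.2 + 30)/1800 = 7.4%. The two standard errors are 0.0131 and 0.0120, so the right side is 0.0257 + 0.0101 = 0.0358, or about 3.6 points.

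| Assumed CMT risk | SE (points) | 95% half-width (points) | Excess with 80% power (points) |
|---|---|---|---|
| 3% | 0.85 | 1.7 | about 3.0 |
| 5% | 1.09 | 2.1 | about 3.6 |
| 10% | 1.50 | 2.9 | about 4.6 |
| 20% | 2.00 | 3.9 | about 5.9 |

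These are simple proportions with complete follow-up. Staggered entry and withdrawal would widen the intervals somewhat.

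**The case against.** **Some harm is compared between the arms.** This is true. All-cause mortality has a boundary favouring medical therapy, and healthcare utilization covers both arms. Neither gives the rate of a non-fatal stroke, syncope, infection or bleed by arm.

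**Safety is watched.** The DSMB reviews safety issues (14.2), and the sponsor reviews aggregate adverse event rates and passes concerns to the DSMB (22.1). It would therefore be wrong to say that an excess must go unnoticed or unreported. These are monitoring activities, though, and not a pre-specified estimate in the final report.

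**A stronger reading.** A reader might infer that these events are reported only when an unblinded site blames the device. The documents do not support this.
- Section 20.1 requires reporting whatever the cause.
- Treated VT/VF and inappropriate shocks are analysed with no relatedness condition, so an induced ventricular arrhythmia that the device treats would be counted.
- Section 20.3 says "The Investigator must assess the relationship of the AE to the study device as related or unrelated", but no section says that the complication summary uses that call. Table 20.2-1 also holds a separate complication and Type I–IV classification for FDA reporting. Dependence on site attribution is a reasonable inference for that one summary, not a stated rule.
- Section 20.3 asks for two categories while Table 20.3-1 gives five. That needs reconciling, but it is a separate drafting matter.

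**Ascertainment differs by arm.** This stands and limits what should be compared. At one month S-ICD subjects are seen in clinic and CMT subjects are telephoned. Annual visits must be in clinic for S-ICD subjects but may be by telephone for CMT. For ventricular arrhythmia the problem is decisive. Only S-ICD subjects have a recorder, and VF that the device terminates would count as a non-fatal event, while untreated VF in a CMT subject may appear as a death. An apparent excess could reflect device benefit.

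**Conclusion.** The concern holds: the plan pre-specifies no by-arm summary of serious or cardiovascular adverse events, although both arms supply the data. For stroke, syncope, infection and bleeding, the planned analyses do not estimate the excess over CMT that would reveal a device effect.

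Under the assumed risks of 3% to 20%, such an estimate would have a 95% half-width of about 1.7 to 3.9 points. It would have 80% power for excesses of about 3.0 to 5.9 points. That is useful for common serious events and weak for rare ones. These figures rest on 1,200 and 600 subjects and on event risks that the documents do not give.

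The primary endpoint, its boundaries and its power are untouched. The change should be made, but the mortality result does not depend on it.

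**What to change.** In Sections 6.3 and 12.3.1, add a descriptive safety analysis in all randomised subjects, by assigned arm and regardless of attributed relationship, labelled exploratory.

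- **Events:** any serious adverse event, and serious stroke, syncope, infection and bleeding separately.
- **Estimates:** cumulative incidence from randomisation with death as a competing event, and the between-arm difference with a 95% confidence interval. Because Section 20.1 records death as the outcome of a serious adverse event, state that an event ending in death counts as the event, and that only death without it competes.
- **Not compared:** ventricular arrhythmia, which stays in the S-ICD-only analyses. Any atrial arrhythmia comparison needs the same ascertainment caution.
- **Unchanged:** the three S-ICD-only device analyses.

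Specify this before anyone drafting it has seen results by arm.

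The cost is SAP wording and one set of tables from forms already collected. Endpoint, alpha, sample size and patient care do not change. The downside is that clinic rather than telephone follow-up may raise ascertainment in the S-ICD arm. Restricting the comparison to serious events, and the record reviews required in both arms (11.8, 11.9.1, 11.9.2), limit this. What remains would tend to count against the device and should be stated beside the results.

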#### 4. Introduction

Implantable cardioverter defibrillators (ICD) and more recently the subcutaneous ICD (S-ICD) have been shown to be effective in preventing sudden cardiac death in high-risk cardiac patients. The MADIT II trial previously demonstrated a significant reduction in all-cause mortality with an ICD implantation compared to optimal medical therapy (hazard ratio 0.69; 95% CI 0.51 to 0.93; two-sided P=0.016) in high-risk cardiac patients with prior myocardial infarction and severely impaired left ventricular ejection fraction (LVEF  $\leq$  30%).

However, patients with severely impaired LVEF represent only a minority of patients at risk for sudden cardiac death (SCD). Other cohorts at high risk for SCD who could potentially benefit from an ICD include patients following a coronary event, especially those with other clinical risk factors, such as age or diabetes mellitus (DM).

Diabetes mellitus has been shown to be associated with increased risk for SCD following a myocardial infarction, independent of the infarct size and LVEF, but is not currently used in the indication for ICD implantation. Data from a substudy of the VALIANT trial, which enrolled 11,000 subjects (3,095 diabetics), indicate that diabetes was associated with a 37% higher risk of all-cause mortality, independent of LVEF, (adjusted hazard ratio of 1.37, 95% CI 1.25-1.51) compared to non-diabetics. The mortality risk in diabetic patients with LVEF >39% was similar to the mortality risk in non-diabetic patients with LVEF in the 30% range. This observation was further supported by another large clinical study, the Candesartan in Heart Failure – Assessment of Reduction in Mortality and Morbidity (CHARM) program^11, and by smaller single and multicenter studies. The large multi-center study assessing 3276 post infarction patients from Germany and Finland showed that the incidence of SCD was significantly higher in diabetic versus non-diabetic patients with an LVEF >35% (HR 3.8 (95% CI 2.4-5.8; p<0.001), and the incidence of SCD in diabetic patients with LVEF >35% was similar to the incidence in non-diabetic patients with an LVEF  $\leq$  35% (4.1% vs 4.9%, respectively).

These data indicate that post-MI diabetic patients have a significant risk for SCD even with a relatively preserved LVEF, and present a population with a significant unmet need that could potentially be addressed with an expanded ICD indication. This may have an important global health impact and clinical implications. Diabetes is currently one of the most prevalent, major health issues in the United States and throughout the world. It is estimated that DM affects nearly 29 million people in the United States alone and claims more than 250,000 lives annually, with higher mortality risk in those older than 60 years of age; furthermore, the prevalence of diabetes is expected to increase dramatically in the US and worldwide in the near future.

Therefore, the MADIT S-ICD study was designed to prospectively test the hypothesis that post-MI diabetic patients with a relatively preserved left ventricular ejection fraction (LVEF 36-50%) will demonstrate a lower rate of all-cause mortality with an S-ICD than in those who do not receive an S-ICD. The S-ICD was chosen for this study design due to device system characteristics that could potentially provide advantages in diabetic patients who may otherwise be at a higher risk for device-related infections.

